## PROTOCOL TITLE: Aromatherapy on Tower 4 (Non-Otolaryngology)

1. Total anxiolytic medication use
2. Total antiemetic medication use
3. Total opioid medication use
4. Observed and patient-reported sleep.
5. Patient-reported patient satisfaction
6. Patient-reported well-being

### 7) Procedures Involved

#### Methods:

Staff education will be completed prior to the start of the study. Staff will watch a short instructional video. <https://vimeo.com/276457486>. They will then practice how to open the Elequil tabs. Staff will be educated on how to introduce the study to eligible patients.

Upon admission to Tower 4 - an acute care, remotely monitored telemetry unit at UC Davis Medical Center in Sacramento, CA., the bedside RN will introduce the study to the patient. If they are interested in participating, the patient will be evaluated by a member of the research team on whether they meet the inclusion criteria to participate in the study. If inclusion data is met, the research team member will fully introduce and explain the study to the patient. If the patient is interested in participating in the study, the research team member will consent the patient.

After consent is obtained, a baseline assessment tool will be given to the subject for completion, asking them to rate their pain, anxiety and/or nausea using a Likert scale.

Upon completion of these assessment tools, the subject will be asked to identify their highest priority among the symptoms ranked to which they will then be given the corresponding aromatherapy tab to treat that symptom.

The research team member will then provide the tab that is identified to treat that symptom.

- Lavendar: Promotes relaxation, comfort, and sleep. Assists with decreasing anxiety.
- Lavendar-sandalwood: Promotes relaxation, comfort, and sleep. Assists with aches and restlessness.
- Lavendar-peppermint: Promotes relaxation during pain, calm

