## 2) Objectives

The purpose of the study is to investigate the effects of aromatherapy on pain, anxiety, and nausea in patients on an acute care unit. The primary objective of this project is to determine whether Elequil aromatherapy tabs show a measurable benefit in reducing patient reported pain, anxiety, and nausea, thus reducing the use of anxiolytic, antiemetic, or opioid medications. The secondary objective is to identify the effectiveness of aromatherapy on improved sleep and improved patient satisfaction and well-being.

Aromatherapy has been studied and shown effective for the decreased effects of pain, anxiety, and nausea. We are hypothesizing that the use of aromatherapy has a positive effect in decreasing patient-reported pain, anxiety, and nausea, and increasing sleep and overall patient satisfaction.

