### Inclusion criteria:

- Age 18 years or older
- Admission to Tower 4 for an anticipated inpatient stay >24 hours
- Alert and oriented
- Capable of using a visual scale to self-report symptoms
- Naïve to the use of aromatherapy for the use of decreasing pain, anxiety, and/or nausea to participate.
- Not on a pediatric service

The specific criteria for subject selection are patients admitted to Tower 4, an acute care/telemetry unit, who are conscious and able to communicate, that understands the purpose of the study and is competent and can give consent. The patient must not include any of the following:

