### 6) Study Endpoints

**Primary endpoint:** Elequil aromatherapy tab use is effective on

1. Patient-reported pain score
2. Patient-reported anxiety score
3. Patient-reported nausea score

**Secondary endpoints:** Elequil aromatherapy tab use is effective in decreasing the following as measured by the corresponding scales:

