## PROTOCOL TITLE: Aromatherapy on Tower 4 (Non-Otolaryngology)

anxiousness, and soothe queasiness.

- Orange-peppermint: Uplifts, energizes, and soothes queasiness/nausea.

Subjects will have the option of choosing how much scent they receive by determining how much of the essential oil pad is exposed. MAX SCENT will be used for the full effect of the essential oil or MIN SCENT for a lighter effect of the essential oil. The aromatherapy tab will then be attached to the front of the patient gown in the proximity of the clavicle area. It should not be placed directly on skin.

1. Recruitment of participants
2. Consent of participants
3. Baseline survey completion and assessment
  - a. Demographic characteristics of subjects (age, gender)
  - b. Baseline assessment scores
    - i. Likert Scales
4. Offer of aromatherapy tab to participant
5. Application of aromatab to the patient's gown or clothing in the proximity of the clavicular area
6. Assessment/observation after 8 hours of application to a maximum of 24 hours
  - a. Anxiety
  - b. Pain
  - c. Nausea
7. Removal of aromatherapy tab after a maximum of twenty-four hours
8. Follow up survey completion after 8 hours.
  - a. Follow up assessment scores.
    - i. Likert Scales
9. Additional data retrieval (from medical chart in the EMR)
  - a. Anxiolytic medication use

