## PROTOCOL TITLE: Aromatherapy on Tower 4 (Non-Otolaryngology)

### Assessment Tools

**Anxiety Likert Scale:** This one-item scale consisted of five evenly spaced numbers each anchored to a level of anxiety (0 = not at all anxious, 2 = a little anxious, 3 = moderately anxious, 4 = very anxious, 5 = extremely anxious).

**The Numerical Rating Pain Scale** measures pain experienced right now based on a 11-point Likert scale with choices of 0 = no pain, 5 = Moderate pain, 10 = Worst possible pain. We will be utilizing this 0-10 scale for pain because it is one of the most commonly used pain scales that is used at the bedside.

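### The baseline instruction lets a primary-endpoint symptom go unrated at Hour 0; if absent symptoms are the ones skipped, within-subject change leans toward improvement

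*Protocol*

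**What the plan says.** - **Objective (Protocol Section 2).** The tabs are to "show a measurable benefit in reducing patient reported pain, anxiety, and nausea".
- **Primary endpoints (Section 6).** Three separate scores are listed: pain, anxiety and, as the third, "Patient-reported nausea score".
- **Baseline (Section 7, Methods).** After consent the subject receives a tool "asking them to rate their pain, anxiety and/or nausea using a Likert scale". Then "the subject will be asked to identify their highest priority among the symptoms ranked", and the tab is matched to that choice.
- **Procedure list (Section 7).** Step 3b says only "Baseline assessment scores", with Likert scales beneath it. Step 6 reads "Assessment/observation after 8 hours of application to a maximum of 24 hours" and lists anxiety, pain and nausea, with no option to rate only some.
- **Entry (Section 4).** The symptom-related criterion is "Capable of using a visual scale to self-report symptoms". No minimum score is required on any symptom.
- **Scales (Assessment Tools).** Each scale has a zero for a symptom-free subject; for anxiety it is "0 = not at all anxious".
- **Analysis (Section 7, step 10).** The protocol names who will analyse the data. It gives no test and no rule for missing scores.

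**The concern.** The same three primary endpoints are specified differently before and after application. The Methods sentence is the only place that says which symptoms are rated at baseline, and a subject who rates one or two of them has complied with it. Because entry requires no symptom, some enrolled patients will probably lack one or more of the three, so the question will arise in practice.

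Every subject is offered a tab and no control group is described. A reduction can then be shown only against the subject's own Hour 0 score. A symptom with no such score yields no change, and if it appears later that worsening is not counted. If the unrated symptoms are mostly absent ones, the pairs left over are those whose score could fall. Nothing in a one-group design offsets that selection, and an analysis plan cannot recover a rating that was never taken.

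**Working it through.** The protocol gives no figure to reproduce: it states no alpha, SD, effect size or symptom prevalence, and the enrolment goal of 100 has no derivation. The check is of the mechanism and its possible size.

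**Inputs.** From the protocol: 100 subjects, and scales of 0-5 (nausea; anxiety approximately, since its description gives no anchor for 1) and 0-10 (pain). Assumed: no treatment effect and no drift; 20%, 40% or 60% scoring 0 at baseline; latent correlation of 0.5 or 0.8 between baseline and follow-up; none, half or all of the zero scorers leaving the item unrated; two-sided 5% one-sample t test on the change scores.

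**Identity.** Let p be the share scoring 0 at baseline, m the mean change in those above 0, and s the share of zero scorers who skip. With no effect, the mean change over all subjects is 0, so zero scorers must on average rise by −m(1−p)/p. Then:

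- pairs kept = 100 × (1 − s·p)
- mean change in kept pairs = m × s(1−p) / (1 − s·p)

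At s = 0 the mean change is 0; at s = 1 it is m.

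**Simulation, 0-5 score, 1,500 runs per setting.** False benefit means p < 0.05 with a falling mean.

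| Zeros | Correlation | Half skip: pairs | mean change | false benefit | All skip: pairs | mean change | false benefit |
|---|---|---|---|---|---|---|---|
| 20% | 0.5 | 90 | −0.137 | 11.7% | 80 | −0.303 | 33.3% |
| 20% | 0.8 | 90 | −0.060 | 6.6% | 80 | −0.132 | 15.3% |
| 40% | 0.5 | 80 | −0.250 | 20.1% | 60 | −0.657 | 72.5% |
| 40% | 0.8 | 80 | −0.110 | 11.1% | 60 | −0.302 | 35.7% |
| 60% | 0.5 | 70 | −0.304 | 24.6% | 40 | −1.049 | 86.7% |
| 60% | 0.8 | 70 | −0.146 | 13.4% | 40 | −0.522 | 50.6% |

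**Cross-check.** For 40% zeros and correlation 0.5, m = −0.657. With half skipping, the identity gives −0.657 × (0.5 × 0.6)/(1 − 0.2) = −0.657 × 0.375 = −0.246, against −0.250 simulated.

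**Simulation noise.** The standard error of the 24.6% entry is √(0.246 × 0.754/1500) = 0.011. Repeat runs of the same model put that upper end between 23% and 25%.

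**0-10 score.** If all zero scorers skip, the mean change is −0.222 to −1.906 and false benefit 12.9% to 81.1%. If half skip, it is −0.099 to −0.524 and 6.0% to 20.3%.

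**Nobody skips, zeros recorded.** All 100 pairs remain, the mean change is about 0, and the test rejects in about 4-7% of trials in both directions together (nominally 5%, so about 2.5% toward benefit).

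**Skipping unrelated to severity.** The kept pairs are then a random subset. Precision is lost but the expected change stays at 0.

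**The case against.** The best reply is that full rating is already intended. The tool is handed over to be completed, and Section 5 likewise calls for a completed tool at Hour 0. Steps 3b and 8a describe baseline and follow-up scores in parallel terms. Choosing a priority symptom presupposes ratings of more than one. All three scales offer a zero, and the protocol uses the same loose conjunction in its inclusion criteria and in Section 12, where it sets no rule about skipping items. This shows that full rating is possible and perhaps meant. It does not make it required: no passage says which items make the tool complete or that a symptom-free subject must record 0.

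The nausea scale notes describe nurses recording a rating before a non-drug intervention, so a nausea baseline might exist in the chart. However, the record items listed in step 9 do not include those ratings.

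A reader might go further and infer that the protocol itself drops symptom-free subjects from a paired primary analysis. The documents do not support that. They do not say that symptoms will be skipped or by whom, and they name neither a paired test nor a complete-case rule; those choices may sit in an analysis plan not shown. Nor are the high false-benefit rates a property of the plan: they belong to the extreme case in which every zero scorer skips.

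**Conclusion.** The point holds in conditional form. The wording allows a primary symptom to have no Hour 0 score, at odds with the three-symptom list after application. If the skipped symptoms are mainly absent ones and change is computed in those with a baseline score, the result leans toward improvement.

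On a 0-5 score with no true effect, false benefit runs from about 15% to 87% of trials if every zero scorer skips, and from about 7% to 25% if half do. Prevalence of zeros, retest correlation and skipping behaviour are all assumptions, so these ranges show what could happen and do not estimate this trial's error rate. The change is still worth making before data are collected, because the missing score cannot be restored later and baseline is the only comparator.

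**What to change.** In the Section 7 Methods sentence, replace the and/or list with: *pain, anxiety and nausea; every subject rates all three, recording 0 where the symptom is absent*. Apply the same requirement at Hour 0 and at each completed follow-up, and name the three symptoms under step 3b so that it matches step 6.

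The cost is one wording change, carried through to the form and staff instructions; the scales already exist. If full rating was always intended, the edit only confirms it. It removes this selection bias alone. Scores that fall under usual care or by regression to the mean would still look like benefit in a one-group study, and the 4-7% rejection rate shown for complete rating assumes no such drift.

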## PROTOCOL TITLE: Aromatherapy on Tower 4 (Non-Otolaryngology)

anxiousness, and soothe queasiness.

- Orange-peppermint: Uplifts, energizes, and soothes queasiness/nausea.

Subjects will have the option of choosing how much scent they receive by determining how much of the essential oil pad is exposed. MAX SCENT will be used for the full effect of the essential oil or MIN SCENT for a lighter effect of the essential oil. The aromatherapy tab will then be attached to the front of the patient gown in the proximity of the clavicle area. It should not be placed directly on skin.

1. Recruitment of participants
2. Consent of participants
3. Baseline survey completion and assessment
  - a. Demographic characteristics of subjects (age, gender)
  - b. Baseline assessment scores
    - i. Likert Scales
4. Offer of aromatherapy tab to participant
5. Application of aromatab to the patient's gown or clothing in the proximity of the clavicular area
6. Assessment/observation after 8 hours of application to a maximum of 24 hours
  - a. Anxiety
  - b. Pain
  - c. Nausea
7. Removal of aromatherapy tab after a maximum of twenty-four hours
8. Follow up survey completion after 8 hours.
  - a. Follow up assessment scores.
    - i. Likert Scales
9. Additional data retrieval (from medical chart in the EMR)
  - a. Anxiolytic medication use

## PROTOCOL TITLE: Aromatherapy on Tower 4 (Non-Otolaryngology)

- b. Pain relieving medication use
- c. Antiemetic medication use
- d. Medication use for treating insomnia.
- e. Patient report of satisfaction on exit survey

### 10. Data analysis

The collected data will be analyzed by the study team in consultation with [name], CTSC Statistician, and [name], Clinical Nurse Scientist.

### 11. Reporting/dissemination

The deidentified information and findings collected from this study will be reported/disseminated with stakeholders within the institution. Investigators also intend to disseminate findings on a broader scale (e.g., professional meeting presentation, publication).

## **8) Data and/or Specimen Management and Confidentiality**

Individual's responses/statements will not include any information that identifies the individual, but the responses/statements will be coded and linked to their identity on a separate document or in a separate database.

All identifiable electronic data will be maintained on an encrypted device requiring a password for access. Passwords will not be shared and will be protected from access.

I understand that if this study involves the use of the UC Davis Health Electronic Health Record (EMR/EPIC) which also contains the clinical data for Marshall Medical Center (MMC), that MMC patient data cannot be accessed for research purposes and that I must take the necessary steps to ensure that MMC data is not accessed, used, or disclosed for UC Davis Health research purposes. Identifiable information from medical records will be stored on a password protected, encrypted device. Investigators will follow applicable university policies (UC Davis Hospital Policy 1313, UCDHS P&P 23002499, and UC Business and Finance Bulletin on Information Security (IS-3).

All paper records will be stored in a locked room/file-cabinet with access limited to only individuals who have a right and need for access.

## **9) Data and/or Specimen Banking**

Data will not be banked.

## 10) Withdrawal of Subjects

Subjects may withdraw consent at any time, and they will be reassured that their clinical care will not be compromised if they were to withdraw. Subjects will be withdrawn from the study for the following reasons:

- Subject changes their mind and decides to opt out of the study before utilizing aromatherapy.
- Development of an allergic reaction (rash, indurations, increased discomfort, anaphylactic symptoms) to the use of aromatherapy
  - The aromatherapy tab will be removed and sequestered so as to not be used again.
  - Subject will be monitored with provider notification of patient's allergic reaction.
- Hospital discharged within 12 hours of admission.
  - Aromatherapy tab will be removed before discharge.
  - Subject will be asked to complete the survey, and the time of completion (since aromatherapy initiated) will be noted.
- Transferred off the unit (to ICU or a different unit)
  - Aromatherapy tab will be removed before transfer.
  - Subject will be asked to complete the survey, and the time of completion (since aromatherapy initiated) will be noted.

Subjects are free to withdraw from the study at any time upon request. Subject participation in the study may be stopped at any time at the discretion of the Investigator or Attending Physician. When a subject withdraws from the study, the reason(s) for withdrawal will be recorded by the Investigator.

## 11) Risks to Subjects

Even though the products that will be used are diluted and we will not be applying concentrated solutions directly to the skin, the following are identified risks related to aromatherapy use:

- Allergic reaction to the use of aromatherapy, including the development of
  - Dermatitis

## PROTOCOL TITLE: Aromatherapy on Tower 4 (Non-Otolaryngology)

- Runny nose/nasal congestion (sinus issues)
- Rash
- Red or bumpy skin (indurations)
- Increased discomfort
- Anaphylactic symptoms

The rates of allergic reactions for each essential oil that will be used for this study are as follows:

Sandalwood: 0.9%, orange and peppermint: 0.6%

Lavender: 2.2%

The patient will notify the nurse immediately if any of these symptoms appear.

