### 5) Study Timelines

Participants of the study will ideally wear the aromatherapy tab on their gown for at least 8 hours to assess its effectiveness. After a minimum of 8 hours has elapsed, they will be given a follow up assessment tool to evaluate their symptoms and their experience in using aromatherapy.

- Identification of eligibility
- Consent
- Assessment 1 (Hour 0)  
Awake - complete assessment tool.
- Aromatherapy tab application
- Assessment 2 (Hour 8)  
Sleeping - no assessment/document sleep  
Awake – complete end assessment tool.  
Satisfaction assessment

If patient prefers, they can continue to utilize aromatherapy, otherwise tab is to be removed, and study is complete.

- Assessment 3 (Hour 12-24)
- Aromatherapy tab removal (after the maximum 24 hours worn)
- Additional data collection as noted below (medication use)

Individual subject participation will total up to 8 hours to a maximum of twenty-four hours.

We anticipate that our goal enrollment of one hundred subjects will be accomplished within six months (from first subject enrolled to last subject). Our total estimate for study completion is twelve months.

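### Allergic reactions are never actively asked about: capture rests on the patient volunteering them and then being withdrawn, so a count of zero could reflect not asking

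*Protocol*

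**What the plan says.** Protocol Section 11 (Risks to Subjects) lists six signs of an allergic reaction: dermatitis, nasal symptoms, rash, red or raised skin, more discomfort, and anaphylaxis. It gives rates of 0.9% for sandalwood, 0.6% for orange and peppermint, and 2.2% for lavender. On detection it says only: "The patient will notify the nurse immediately if any of these symptoms appear".

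Section 7 (Procedures Involved) itemises what is collected. Step 6 is "Assessment/observation after 8 hours of application to a maximum of 24 hours", and the items under it are anxiety, pain and nausea. Step 8 is the follow-up survey with the Likert scales. Step 9 retrieves four classes of medication and satisfaction.

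Section 5 (Study Timelines) adds sleep and satisfaction. It describes the follow-up tool as covering symptoms and experience with the product. A subject asleep at Hour 8 is not assessed at that point. It then says: "If patient prefers, they can continue to utilize aromatherapy, otherwise tab is to be removed, and study is complete".

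Section 10 (Withdrawal of Subjects) makes one reason for withdrawal "Development of an allergic reaction (rash, indurations, increased discomfort, anaphylactic symptoms) to the use of aromatherapy". The tab is removed, the subject is monitored and the provider is told. It adds: "When a subject withdraws from the study, the reason(s) for withdrawal will be recorded by the Investigator". For a subject who leaves the unit, "Aromatherapy tab will be removed before transfer", and the subject is asked to complete the survey. The same applies to early discharge.

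**The concern.** The protocol treats allergic reaction as the main risk and puts rates on it, yet schedules no question about it. Recording depends on a chain: the patient notices a sign, links it to the tab, tells a nurse, is recognised as meeting the withdrawal criterion, and is withdrawn with the reason noted. A mild reaction can drop out at any link.

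Section 7 also separates the bedside nurse from the research team. No sentence requires the nurse who is told to pass the report to the study. The staff training described there covers a video, handling the tab and introducing the study; reporting of reactions is not named.

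The investigators intend to publish. Benefit and satisfaction would be measured by questionnaire while harm was left to spontaneous report, and readers could take a count at or near zero as a measured result. What is collected from subjects is protocol content, so an analysis plan would not fill this gap.

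**Working it through.** **Step 1. Where a reaction could enter the data.**

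| Place in protocol | What is collected | Reaction asked about? |
|---|---|---|
| Section 5, Hour 8 and Hour 12-24 assessments | symptoms, experience, sleep, satisfaction | no item named |
| Section 7, step 6 | anxiety, pain, nausea | no |
| Section 7, step 8 | Likert scales | no |
| Section 7, step 9 (chart) | four medication classes, satisfaction | no |
| Section 10 | reason for withdrawal | yes, once noticed and acted on |
| Section 11 | patient tells the nurse | passive only |

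**Step 2. The two lists of signs.** Section 11 has six signs. The bracketed list in Section 10 has four: rash, indurations, increased discomfort and anaphylactic symptoms. Dermatitis and nasal symptoms appear only in Section 11.

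**Step 3. Timing.** For a subject who does not continue, the study ends when the tab comes off. Monitoring after removal is stated only for a subject whose reaction has already been noticed. For everyone else, no step looks for a later onset.

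**Step 4. Scale.** The protocol states no expected number of reactions, so there is no figure to reproduce. Inputs are N = 100 (Section 5: "our goal enrollment of one hundred subjects will be accomplished within six months") and the Section 11 rates p. The assumptions are that all 100 subjects are exposed to the oil in question and that the quoted rate applies to each of them.

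Expected number = N × p. Chance of at least one = 1 − (1 − p)^100.

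| Rate p | Expected | Chance of at least one |
|---|---|---|
| 0.6% (orange and peppermint) | 100 × 0.006 = 0.6 | 1 − 0.994^100 = 0.45 |
| 0.9% (sandalwood) | 100 × 0.009 = 0.9 | 1 − 0.991^100 = 0.60 |
| 2.2% (lavender) | 100 × 0.022 = 2.2 | 1 − 0.978^100 = 0.89 |

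**Step 5. Effect of incomplete reporting.** The share of reactions that patients volunteer is unknown. As an illustration only, suppose it is half. The chance of recording none is then (1 − 0.5p)^100:

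- p = 2.2%: 0.989^100 = 0.33, against 0.978^100 = 0.11 if every reaction is captured.
- p = 0.6%: 0.997^100 = 0.74, against 0.994^100 = 0.55.

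**Step 6. What a true zero would show.** With every subject asked and none of 100 reacting, the one-sided 95% upper limit is 1 − 0.05^(1/100) = 2.95%. That is above the quoted lavender rate of 2.2%, so even a measured zero says little. A zero obtained without asking says less.

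**The case against.** The strongest reply is that Section 10 already does much of the work. Withdrawal for an allergic reaction is mandatory and the investigator records the reason, so a recognised reaction does leave a study record. A reader might infer that the study records no reactions at all, or that observation of every subject stops when the tab comes off. The protocol supports neither reading. A subject with a noticed reaction is monitored afterwards, and subjects transferred or discharged early are asked to complete the survey first. Subjects asleep at Hour 8 are not necessarily missed either: step 8 places the survey after 8 hours, and an Hour 12-24 assessment is listed.

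The form itself is not reproduced, and its part on experience with the product might prompt some reports. The bracketed list in Section 10 may be meant as examples, and rash overlaps with dermatitis.

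The rates are also a weak forecast. By their titles, the cited sources concern fragrance-sensitive patients and a clinic series on contact allergy. Here the product is diluted and kept off the skin, and people with known allergy or sensitivity are excluded. Tabs are assigned by priority symptom across four scents, so no single oil need reach all 100 subjects.

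Finally, no safety endpoint is declared. A reader might conclude that the trial fails to support the protocol's minimal-risk statement, but that is a prospective judgement in the section on compensation for injury, not a conclusion the data were meant to deliver.

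These points limit the claim but do not remove it. Each existing contact with the subject is a chance to ask, and no listed item does so.

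**Conclusion.** The point holds in a limited form. Reactions are not actively elicited at any scheduled assessment or in the chart retrieval. They reach the study only through self-report followed by withdrawal with a recorded reason. Signs found only in Section 11, and reactions that first appear after removal in a subject who had reported none, have no stated capture.

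The size is small in absolute terms: 0.6 to 2.2 expected reactions in 100 subjects. This rests on applying contact-allergy rates to this use and on exposing everyone to one oil. The 0.45 and 0.89 chances of at least one reaction rest on the same assumptions and should not be read as predictions. The share of reactions missed is unknown. What can be said is that with counts this low, one or two missed reactions could decide whether the report shows zero. This is a worthwhile improvement in how harms are ascertained. It does not bear on the efficacy endpoints.

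**What to change.** 1. Add a yes/no checklist of the Section 11 signs to the existing follow-up survey. Use it for every subject, including at the survey already planned for early discharge or transfer. Ask it after waking for subjects asleep at Hour 8.
2. Add to Section 7 step 9 an item for any reaction documented in the chart from tab application to hospital discharge. This covers onset after removal while the subject is still an inpatient.
3. Report the number of subjects with a reaction by tab type, out of all who wore a tab.
4. Reconcile the lists of signs in Sections 10 and 11. Which signs should lead to withdrawal is for the investigators to settle.

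The cost is a few check boxes and one more item in a chart review already planned. The form becomes slightly longer and the harm count may look less favourable. Some positive answers will be unrelated to the tab, since nasal symptoms and discomfort are not specific to it. Whether departing subjects already receive a number to call cannot be judged from the protocol text, so no change is proposed there.
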